#### 7.3.3 Moxifloxacin: Safety and tolerability

Data on the long-term use of MXF show that it has an excellent safety profile [47]. Comprehensive safety data is available from Phase II to Phase IV studies performed by Bayer Healthcare, comparing MXF to a comparator group of patients receiving various other antibiotics. 23.9% of patients suffered adverse drug reactions (ADRs) due to oral application of MXF, while 22.0 % of patients in the comparator group suffered such reactions [48]. Nausea (7.5%) and diarrhoea (5.8%) are the most frequent individual AEs reported for MXF, but also for the comparator group. Nausea is more common in the MXF group. All other AEs differ by less than 1% between the treatment groups. Headache (4.4%) and dizziness (3.6%) were third and fourth most frequently encountered AEs in patients with oral MXF. Among 13.368 patients who received the drug via oral route, 3 fatal ADRs were registered. Among 1.144 patients who received the drug via intravenous route, no fatal ADRs were registered. In PO active-controlled studies, 38 of the 10,613 MXF-treated patients (0.4%) and 51 of the 10,685 comparator recipients (0.5%) had at least 1 AE with fatal outcome. Myocardial infarction and septic shock (reported in 5 patients each) are the most frequent AEs leading to death. Serious adverse drug reactions (SADRs) were reported in 59 (0.6%) and 53 (0.5%) of MXF and comparator-treated patients, respectively. The most common SADRs are abdominal pain and vomiting, reported with an incidence <0.1%.

## 7.4 Combination of drugs used in the study

Three of the drugs used in this study have the potential to increase cardiac QT intervals, which has in the past discouraged large-scale use of these drugs together in a regimen. We provide recent data below to suggest that these drugs have been combined safely:

Best evidence on this question is available from the prospectively randomized ACTG 5343 (DELIBERATE) trial. This trial compared MDR-TB treatments containing either BDQ or DLM alone, or both drugs in combination, over a treatment period of 24 weeks.

The study found a mean change in QTcF from baseline of 11.9 ms (95% CI: 7.4 - 16.5) in the BDQ arm, 8.6 ms (4.0 - 13.2) in the DLM arm, and 20.7 ms (16.1 - 25.4) in the BDQ+DLM arm [49].

The combined effect on the QTcF interval of co-administration of bedaquiline and delamanid was clinically modest and no more than additive. This study demonstrated the cardiac safety of the combined use of these drugs in patients with MDR-TB taking MBT with normal baseline QTcF values.

These data from a randomized study are corroborated by a meta-analysis by the group of Migliori et al. analysed combined treatment of drug-resistant TB with BDQ and DLM in Armenia, France,

India, Latvia, Russian Federation, South Africa, South Korea, and The Netherlands. This review is the largest up to date, and included 87 cases of 7 different studies, of which 54.5% of patients suffered from XDR-TB and 27.3% were HIV co-infected. The study concluded the following: Most M/XDR patients were concomitantly treated with BDQ and DLM, and in most cases for a duration > 6 months. The sputum culture conversion rate after 6 months of treatment was considerably higher (81.4%) than historical M/XDR-TB patient cohorts. Out of 87 patients, 23 (26.4%) showed >1 episode of QT prolongation >450 ms in men or 470 ms in women, or a QT increase >60 ms from baseline values, however only 2.3% of treatments were interrupted for the occurrence of life-threatening cardiac adverse events [50].

Médecins Sans Frontières published data on 28 patients receiving BDQ and DLM in combination from South Africa, India and Armenia [51]: 25 of 28 patients received at least one additional QT-prolonging agent, clofazimine or MFX, and 2 patients received both. The key finding from this cohort was that no patient exceeded a QTcF interval of 500 ms, which is the cut-off point best supported as a safety issue by clinical data. Only 4 patients had a change of QTcF >60 ms over their baseline QT interval, and all of them had received clofazimine as QT prolonging agent. In no patient, study drug was permanently discontinued. Of 16 SAEs in 7 patients, 6 were considered possibly related to DLM, BDQ or to both drugs. Eleven SAEs were considered possibly related to other TB drugs. The only fatal event in this cohort was associated with immune reconstitution inflammatory syndrome (IRIS), characterized by acute renal failure and hypoglycaemia. The most common SAE in the cohort was gastrointestinal (4/16, 25%), a common side effect of a number of MDR-TB drugs that may have been part of the regimen (thioamides or para-aminosalicylic acid, PAS). Nervous system disorders accounted for 4/16 SAEs (25%) and psychiatric disorders 2/16, (12%). Both SAEs are commonly associated with cycloserine, another drug commonly used in MDR-TB regimens. Of note, 23 (82%) patients in this report received LZD as part of their regimen.

Further published case reports include 7 patients: 2 single XDR patients were summarized in a review of case series [52] and 5 more XDR patients' outcomes were published as a separate case series, with patients living in Russia (2), India (2), or the Netherlands (1) [53]. One of 2 in the first case review and 2 of 5 patients in the second case review experienced QTcF >500 ms; in one case prolongation reverted on repeat examination; the second patient was started on concomitant verapamil and had an unspecified dose adjustment. All 3 of the patients exceeding an absolute QTcF prolongation of 500ms had received CFZ as additional QT-prolonging agent in their regimen.

Recent safety data summarized below shows that MXF can also be safely combined with a BDQnitroimidazole combination without exacerbating QT prolongation:

The TB Alliance NC005 study assessed regimens containing BDQ, PTM and PZA, with and without MXF [54]. Published data of QT prolonging effects of PTM 200mg given alone in a 14-day EBA study [55] and DLM in its Phase III study [36] suggests that DLM would not cause more QT prolongation than PTM.

In the regimen containing BDQ+PTM+PZA, the mean QTcF change from baseline was 21.9 ms (95% confidence interval 18.2-25.7), very much in line with that seen for BDQ + DLM in the ACTG 5343 DELIBERATE study mentioned above. In patients receiving MXF in addition to BDQ+PTM+PZA,

QTcF prolongation was unchanged at 21.9 (95% CI 18.7-25.0); so, in this study, there was no difference in QTcF due to the addition of MXF. In the control arm (INH + RIF + PZA + EMB) the mean increase from baseline was 10.2 ms (95% CI 7.0-13.4)[56].

Serious treatment-emergent AEs were equally distributed in the BDQ+PTM+MXF+ PZA group (60 patients) and the BDQ+PTM+PZA group without MXF (59 patients), with 4 events occurring in each arm. The INH+RIF+PZA+EMB arm also had 4 events in 61 patients. In all arms, most patients experienced at least one treatment-emergent AE: 57 of 60 in the MXF-containing arm, 50 of 59 in the arm without MXF, and 44 of 61 in the control arm.

# 8 STUDY OBJECTIVES

# 8.1 Safety and Tolerability Objective:

Overall, the primary objective is to describe the safety, tolerability and exposure-toxicity relationship of DZD given over 16 weeks in combination with standard-dose BDQ, DLM and MXF compared to standard-dose BDQ, DLM and MXF alone.

The aim is to identify the optimal dose of DZD to be used in subsequent studies that provides the best **efficacy at acceptable safety** of the drug when given daily over 4 months in patients with newly diagnosed, uncomplicated, smear-positive, drug-sensitive, pulmonary tuberculosis.

#### 8.1.1 Efficacy Objectives

Primary Efficacy Objective:

• To establish an exposure-response model for DZD, given over 16 weeks in combination with standard-dose BDM, on the change in liquid culture MGIT time to positivity (TTP)

Secondary Efficacy Objective:

- To assess dose and exposure-response relationships for DZD, based on secondary efficacy endpoints, including month-2 culture status in liquid media and on solid media, and time to culture conversion in liquid and on solid media
- To assess the relative efficacy of increasing DZD doses compared to the background regimen without DZD, based on primary and secondary efficacy endpoints.
- To assess the proportion of patients who suffer relapse within 12 months post randomisation, out of those patients completing 16 weeks of therapy and achieving sustained sputum culture conversion, defined as two successive negative liquid media cultures at or before WK08, with no positives to follow by the week 16 visit.

# 8.1.2 Pharmacokinetics Objectives

Primary Pharmacokinetics Objective:

• To describe the pharmacokinetics (PK) of DZD through development of a population PK model

Secondary Pharmacokinetics Objective:

• To describe the PK of BDQ, DLM and MXF including their main metabolites

#### 8.1.3 Mycobacteriology Identification and Characterization Objectives

- To assess the minimum inhibitory concentrations (MIC) of BDQ, DLM, MXF, DZD of the infecting strain.
- To investigate the frequency of acquired mutations in the infecting strain over treatment
- In patients with recurrent disease: comparison of initial and recurrence isolate by whole genome sequencing, to differentiate between relapse and reinfection

# 9 TRIAL ENDPOINTS

#### 9.1 Primary Endpoints

#### 9.1.1 Primary Safety endpoint

Participants will be regularly assessed for AEs during treatment and follow-up phase, including assessments of vital signs, physical examination, weight, detailed neurological examination, colour vision and visual acuity tests, 12-lead ECGs and routine clinical laboratory tests (including chemistry, haematology and urinalysis data).

The safety of DZD will be investigated by evaluation of:

• Proportion of patients experiencing expected oxazolidinone class toxicities, defined as peripheral or optical neuropathy, or incident leukopenia, anemia or thrombocytopenia, or adverse events in line with tyramine pressor response, all of Grade 2 or higher, possibly, probably or definitely related to DZD

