	The safety of DZD will be assessed by evaluation of AEs during treatment and follow-up phase, including assessments of vital signs, physical examinations, weight, detailed neurological examinations, colour vision and visual acuity tests, 12-lead ECG, and routine clinical laboratory tests (including chemistry, haematology and urinalysis data).								
	Primary Safety Endpoint								
	
 
Proportion of patients experiencing expected oxazolidinone class toxicities, including peripheral or optical neuropathy, incident leukopenia, anemia or thrombocytopenia, or adverse events in line with tyramine pressor response, of Grade 2 or higher, possibly, probably or definitely related to DZD
 
								
	Primary Efficacy Endpoint								

The efficacy of DZD will be evaluated by measuring the change in mycobacterial load over									
time on treatment as quantified by time to positivity in BD MGIT 960 ® liquid culture									
described by non-linear mixed-effects methodology									
Secondary Endpoints									
Secondary safety endpoints									
All adverse events									
Adverse events of Grade 3 severity or higher									
Adverse events possibly, probably or definitely related to study drugs									
• Treatment discontinuations or interruptions related to adverse events/serious adverse events									

 
Frequency, severity and type of ECG alterations
 
									

 
Changes in ECG intervals of PR, RR, QRS, QT, Fridericia-corrected QT [QTcF]
 
									

 
Proportion of participants with QTcF > 500ms in ECGs on treatment
 
									
• Proportion of participants with a prolongation of QTcF of grade 3 and above as defined under 14.6.									
Secondary Efficacy Endpoints:									

 
Proportion of patients who suffer relapse, defined as recurrent disease caused by a strain identical to the baseline isolate, within 12 months post randomisation, out of patients completing 16 weeks of therapy and achieving stable culture conversion to negative (SCC) as defined below by week 08, with no positives to follow by the week 16 visit.
 
									

 
Time to recurrent TB, and to relapse, within 12 months post randomisation
 
Time to stable sputum culture conversion (SCC) to negative on liquid media (defined as two negative cultures without an intervening positive culture). Time will be measured as time on treatment until the first negative culture.
 
									

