#### 6.1.4 Delpazolid: Efficacy and safety in clinical studies

DZD has been clinically tested up to Phase 2A with the oral tablet formulation (7 Phase 1 studies-1 study withdrawn and 1 Phase 2a study) and up to phase 1 (1 study) with the intravenous formulation. A total of 239 subjects received DZD, for a maximum administration period of 21 days.

In the single ascending dose study LCB01-0371-11-1-01, the multiple ascending 7-day dose study LCB01-0371-12-1-02 and the multiple ascending 21-day dose study LCB01-0371-14-1-01 the safety, tolerability, and pharmacokinetics of DZD were examined.

Altogether, there were no signs of significant myelosuppression or neuropathy. All ECG results were normal or assessed as not clinically significant. No deaths or SAEs occurred.

In the single-dose phase 1 study DZD was dosed up to 3200 mg. 20 adverse events occurred in 15 subjects. Most AEs were mild; moderate AEs only occurred at 3200 mg.

In the 7-day repeat-dose study, DZD was dosed up to 1600 mg BID. Most AEs were mild. Moderate AEs occurred in the 1600 mg BID group and this group was terminated after the first dose. The maximum tolerated dose in this study was 1200 mg BID.

In the 21-day repeat-dose study, DZD was dosed at a maximum of 1200 mg BID. Most AEs were mild, except for AEs of decreased neutrophil count, abnormal haematology test and abnormal liver function. 1 subject in the 1200 mg BID group showed a low haematocrit 17 days after drug administration and the study drug was discontinued at the discretion of the investigator. A non-compartmental PK analysis was also performed in 28 out of 40 subjects. Accumulation was almost non-existent with multiple dosing.

A food-effect study LCB01-0371-13-1-03 demonstrated a delayed absorption, a decrease in the maximum blood concentration and a decrease of the AUClast by 10%. It was concluded that diet does not have a meaningful influence on treatment.

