#### Screening/Safety laboratory tests

Samples for laboratory tests are to be taken before the day's dose of study treatment is administered.

- Urine:
  - Urine drug screening by a rapid test for opiates, amphetamines, cannabinoids, cocaine, benzodiazepines and barbiturates.
  - Urinalysis\*: Dipstick for pH, protein, glucose, ketones, urobilinogen, blood and leukocytes.
  - $\circ$   $\;$   $\;$  Urine microscopy on abnormal dipstick results as per the investigator's decision.

- Blood:
  - Serum pregnancy test, if female of childbearing potential (SCR, WK09 and WK18)
  - $\circ$  HIV test (CD4 count if HIV positive, additionally viral load, if patient is on ARVs, additionally genotypic resistance testing, if viral load is >1,000 copies/µL) and patient would have to be switched to a non-dolutegravir ART regimen after end of study (SCR)
  - Haematology\*: Complete blood count with differential and platelets
  - Biochemistry\*: ALT, AST, gamma-glutamyl transferase (yGT), alkaline Phosphatase (aP), lipase, direct and total bilirubin, albumin, serum creatinine, electrolytes (Na+, K+, Serum Calcium, Magnesium, Cl-, PO43-), random glucose
  - Coagulation: aPTT, PT, INR

\*performed during safety laboratory assessment, complete list of tests done during screening only

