5.1.1. Primary Safety Endpoint

Participants will be regularly assessed for AEs during treatment and follow-up phase, including assessments of vital signs, physical examination, weight, detailed neurological examination, colour vision and visual acuity tests, 12-lead ECGs and routine clinical laboratory tests (including chemistry, haematology and urinalysis data).

The safety of DZD will be investigated by evaluation of:

Proportion of participants experiencing expected oxazolidinone class toxicities, defined as peripheral or optical
neuropathy, or incident leukopenia, anemia or thrombocytopenia, or adverse events in line with tyramine pressor
response, all of Grade 2 or higher, possibly, probably or definitely related to DZD.

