Table 3.2.18 Summary of Group Mean Platelet Count Changes over time

{Similar shell table as Table 3.2.1}

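### The primary safety endpoint names leukopenia, anaemia and thrombocytopenia but not neutropenia, and the documents disagree on whether that list is closed, so an isolated neutropenia is not counted on a literal reading

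*Protocol*

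**What the plan says.** Protocol 9.1.1 gives the class toxicities as a closed list: "defined as peripheral or optical neuropathy, or incident leukopenia, anemia or thrombocytopenia", followed by events of the tyramine pressor type. Each must be at least grade 2 and judged at least possibly related to delpazolid. SAP 5.1.1 also uses the closed form: "neuropathy, or incident leukopenia, anemia or thrombocytopenia, or adverse events in line with tyramine pressor". The synopsis introduces the same items as examples: "expected oxazolidinone class toxicities, including peripheral or optical neuropathy, incident leukopenia, anemia or thrombocytopenia".

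Neither document gives a laboratory threshold or a list of preferred terms for leukopenia. Severity is graded by reference to CTCAE 5.0 (Protocol 14.6), events are recorded in CTCAE wording where possible (Protocol 14.8), and they are coded by MedDRA preferred term (Protocol 15.3.2, SAP 13.1.2).

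On earlier human data, Protocol 6.1.4 says of the 21-day study: "Most AEs were mild, except for AEs of decreased neutrophil count, abnormal haematology test and abnormal liver function". It gives no counts for these events, and its overall reading of the phase 1 dose studies is that significant myelosuppression was not seen.

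The trial collects the data. Protocol 11.3 includes "Complete blood count with differential and platelets" in the safety laboratory. The haematology shells in SAP Appendix 3.2 have two headings, platelet count and haemoglobin. The table under the haemoglobin heading is titled "Table 3.2.18 Summary of Group Mean Platelet Count Changes over time".

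**The concern.** Protocol 4.2 names suppression of haematopoiesis as one of the two main severe class toxicities, section 5 justifies four months of dosing by the late onset of class toxicity, and section 8.1 ties dose selection to acceptable safety. The haematological part of the composite is there to catch marrow suppression. It lists a low total white count, low red cells and low platelets. It leaves out the one cell line that the protocol itself names as an exception to mild events in the longest study so far.

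If cases are selected by the listed terms, an event recorded under a neutrophil term with no accompanying leukopenia term falls outside the primary endpoint. If they are selected under the synopsis wording, it may fall inside. A primary endpoint should not depend on which page is followed, or on a coding decision taken after the data are seen. No shell in SAP Appendix 3.4 tabulates the primary safety endpoint, so no planned output settles which terms count.

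**Working it through.** The plan states no event rate, power or precision for this endpoint, so there is no figure to reproduce. The check compares the texts and then bounds the effect under assumed rates.

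**The three definitions**

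| Place | Form of list | White cell item | Neutropenia named |
|---|---|---|---|
| Synopsis | open | leukopenia | no |
| Protocol 9.1.1 | closed | leukopenia | no |
| SAP 5.1.1 | closed | leukopenia | no |

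**Can neutrophils fall without the total count qualifying?** Assumed counts, in 10^9/L: neutrophils fall from 4.0 to 1.2, lymphocytes stay at 2.5 and monocytes at 0.7.
- Total before: 4.0 + 2.5 + 0.7 = 7.2.
- Total after: 1.2 + 2.5 + 0.7 = 4.4.

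Neutrophils drop by 70% (2.8/4.0) and the total by 39% (2.8/7.2). Whether 4.4 counts as leukopenia depends on a threshold that the documents do not state.

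**Counts in one arm.** Suppose 3 of 15 patients have a qualifying neutropenia and nobody else has a listed event. If *k* of the 3 also meet leukopenia, the endpoint as written reports *k*/15:
- *k* = 0: 0%
- *k* = 1: 6.7%
- *k* = 2: 13.3%
- *k* = 3: 20%, and nothing is lost.

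**Rates.** Let *b* be the rate of currently listed events, *m* the rate of related grade 2 or higher neutropenia, and *v* the share of neutropenia patients who already have a listed event. With neutropenia named, the endpoint rate is *q* = *b* + *m*(1 − *v*). The chance of at least one event in an arm of 15 is 1 − (1 − *q*)^15. All rates are assumptions.

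| *b* | *m* | *v* | *q* | P(at least 1 of 15), as written | P(at least 1 of 15), neutropenia named |
|---|---|---|---|---|---|
| 5% | 5% | 0 | 10% | 0.54 | 0.79 |
| 5% | 5% | 0.5 | 7.5% | 0.54 | 0.69 |
| 5% | 5% | 1 | 5% | 0.54 | 0.54 |
| 5% | 10% | 0 | 15% | 0.54 | 0.91 |
| 5% | 10% | 0.5 | 10% | 0.54 | 0.79 |
| 5% | 10% | 1 | 5% | 0.54 | 0.54 |

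Over the four delpazolid arms (4 × 15 = 60 patients), the first row means 60 × 0.05 = 3 expected endpoint patients as written, against 60 × 0.10 = 6. The result is driven by *v*, about which the documents say nothing.

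**The case against.** The strongest reply is that little is lost.

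- **Overlap with leukopenia.** Neutrophils are part of the white cell count, so a fall large enough to lower the total can enter as leukopenia. This stands. A reader might infer that neutropenia can never reach the endpoint; the documents do not support that.
- **Other outputs.** All adverse events, those of grade 3 or higher and drug-related ones are secondary safety endpoints. The shells for Tables 3.4.2 and 3.4.3 show events and reactions by preferred term across the five arms, so a neutrophil term would have its own row. SAP 13.2 and Protocol 15.3.3 cover laboratory parameters generically, and the appendix allows its shells to be updated. This also stands: the gap is in the primary endpoint and the planned shells, and the event would not vanish from the report.
- **Strength of the earlier evidence.** A reader might take the 21-day study as showing an established marrow signal. It does not: no counts are given, and the protocol reports no significant myelosuppression. It is a reason to look, and no more.
- **Design choice.** Which toxicities to include is for the sponsor, and the list already touches white cells, red cells and platelets. That is fair, but the documents give no reason for leaving neutropenia out, and they do not agree on whether it is out.

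The laboratory tables matter for a further reason. A laboratory change becomes an adverse event only if the investigator finds it clinically significant (Protocol 14.2 and 14.10), it enters the endpoint only if judged at least possibly related, and physicians know the allocation (Protocol 13.6). A by-arm table of counts does not pass through those judgements. Secondary visibility therefore does not settle what belongs in the primary endpoint.

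**Conclusion.** The point holds in a limited form. On a literal reading of Protocol 9.1.1 and SAP 5.1.1, a delpazolid-related neutropenia of grade 2 or higher is not counted when the total white count does not also qualify as leukopenia. Under the synopsis wording it might be. The effect lies between zero, when every such patient already has a listed event, and the full neutropenia rate, when none does. In the assumed 5% plus 5% case, the endpoint rate with neutropenia named lies between 5% and 10%. These rates are illustrations, because the documents supply none. The conclusion rests on the wording of the three definitions, on preferred-term coding, and on the absence of a stated leukopenia criterion. It does not rest on any claim that delpazolid suppresses neutrophils.

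**What to change.** - **Endpoint wording.** Add neutropenia beside leukopenia, and use the same closed wording in the synopsis, Protocol 9.1.1 and SAP 5.1.1. Do this before the partial database lock after Week 16, when the primary endpoints are analysed.
- **Laboratory shells.** In SAP Appendix 3.2, add tables by arm and visit for total white cell count and absolute neutrophil count.
- **Clerical.** Retitle Table 3.2.18 as haemoglobin, to match its heading.

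The cost is a protocol amendment for wording, an SAP revision and two extra tables. No new samples are needed.

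The downside is that some low neutrophil counts unrelated to delpazolid may be judged possibly related and enter the endpoint. Arm 1 cannot calibrate this within the endpoint: its patients receive no delpazolid, and the open-label endpoint requires relatedness to it. The by-arm count tables, which do not depend on attribution, should be used for the comparison with Arm 1.
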